8.1.2. Display of Adverse Event

Analysis Set: Safety Analysis Set

Analysis Variables: Adverse Event

Category Classification:

Causal Relationship with the Study Drug [Related, Unrelated]

Severity [Mild, Moderate, Severe]

Time of Onset [1<= - <29,
29<= - <57,
57<= - <=Max]

Analysis Methods: For the above analysis items, the following analysis is performed for each treatment group. Analysis variables will be coded using the MedDRA dictionary and be summarized into SOC and PT. SOCs will be sorted in alphabetical order, then PTs will be sorted in frequency order.

- (1) Tabulation of frequencies of all adverse events (by SOC/PT)
- (2) Tabulation of frequency of adverse events with a causal relationship to the study drug (by SOC/PT)
- (3) Tabulation of frequency of all adverse events by severity (by SOC/PT)
- (4) Tabulation of frequency of adverse events with a causal relationship to the study drug by severity (by SOC/PT)
- (5) Tabulation of frequency of adverse events leading to study drug discontinuation (by SOC/PT)
- (6) Tabulation of frequency of serious adverse events (by SOC/PT)
- (7) Tabulation of frequency of Non-serious adverse events (by SOC/PT)
- (8) Tabulation of frequency of serious adverse events with a causal relationship to the study drug (by SOC/PT)

- (9) Tabulation of frequency of serious adverse events leading to study drug discontinuation (by SOC/PT)
- (10) Tabulation of frequency of adverse events leading to death (by SOC/PT)
- (11) Tabulation of frequency of all adverse events by time of onset (by SOC/PT)

Incidence rates will be calculated as following on each analysis.

[Frequency of Subjects]

- Frequency (by SOC/PT)

Within each summary, subjects with one or more adverse events within a level of SOC term is counted only once in that level. Similarly, subjects with one or more adverse events within a level of PT term is counted only once in that level. The denominator when calculating the incidence of adverse events is the number of subjects of safety analysis set.

- Frequency by Severity (by SOC/PT)

Subjects with one or more adverse events within a level of SOC/PT term is counted only once in that level using the most severe incident. The denominator when calculating the incidence of adverse events is the number of subjects of safety analysis set.

- Frequency by Time of Onset (by SOC/PT)

Subjects with one or more adverse events within a level of SOC/PT term is counted only once in that category of time of onset. The denominator when calculating the incidence of adverse events is the number of subjects “whose study drug administration has been continued at that time point and later” or “who experienced an onset of adverse events at that time point or later” in safety analysis set and numerator is the number of subjects “experienced an onset of adverse events at that time point”.

8.2. Other Endpoints and the Analytical Methods

8.2.1. Vital Sign

Analysis Set: Safety Analysis Set

Analysis Variables: Body Weight, Blood Pressure in the Sitting Position (Systolic, Diastolic), Pulse in the Sitting Position

Visit: Start of Treatment Period, Treatment Period 4 week and 8 week

Analysis Methods: The following analysis is performed for Safety Analysis Set.

- (1) Summary statistics of measurements by treatment group at each visit during the treatment period will be calculated and a diagram of the change of individual data will be created.
- (2) The change for each treatment group (Treatment Period 4 week/8 week – Start of Treatment Period) will be calculated at each visit during the treatment period and the same analysis as in (1) will be performed.
- (3) Regarding evaluation results based on standard values, shift tables of start of treatment period and each visit of treatment period 4 week and 8 week will be prepared.

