9.3.4 Completion (Visit 4) or discontinuation

1. Visit 4 shall be the last VISIT, and research subjects shall undergo the following tests at the designated medical institution for FMD measurement within the allowable range of Visit 4 (42 to 70 days after the study drug administration). If the study drug administration is discontinued, research subjects should, to the extent possible, undergo tests within 3 days from the last dose taken.
 - FMD test [fasting and 4-h postprandial (allowable range \pm 30 min)]
 - Laboratory tests [fasting and 4-h postprandial (allowable range \pm 30 min)]
 - Exploratory biomarker evaluation [fasting and 4-h postprandial (allowable range \pm 30 min)]

Food and drink consumption before the visit will be checked.

- Alcohol should not be consumed from 9:00 pm two days before the hospital visit to the time of visit and food should not be consumed from 9:00 pm on the day before to the time of visit.
 - Eating/drinking to excess and extreme change in dietary content should be avoided on the day before the hospital visit.
2. The principal investigator and the investigator shall perform the following tests, observations, and evaluations at Visit 4 (Day 42 to Day 70 days after the study drug administration). If the study drug administration is discontinued, research subjects should, to the extent possible, undergo tests, observations, and evaluations required for the last visit within 3 days from the last dose taken.
 - Physical examination
 - Vital signs
 - Concomitant drugs
 - Study drug compliance
 - Adverse Events

Since the principal investigator or the investigator is required to confirm safety of the tests, observations, and evaluations at Visit 4 or at discontinuation, FMD test and laboratory tests in (1) shall be performed first, and tests, observations, and evaluations in (2) shall be performed last.

At completion of the clinical research, the status of all research subjects administered the study drug shall be recorded on the CRF.

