2. TIME WINDOW

For each inspection, observation and evaluation item, evaluable data is handled according to the following table. When there are multiple data that can be evaluated at the same visit, the one with the closest inspection date, observation, and evaluation date to the reference date is adopted, and if the difference from the reference date is the same, the later data is adopted.

< FMD (Fasting, 4h postprandial) >

| Visit | Reference implementation date | Time Allowance |
|---------------------------|-----------------------------------|-------------------------------|
| | | Days after the Administration |
| Start of Treatment Period | Days after the Administration: -1 | -15 to -1 |
| Treatment period 4 week | Days after the Administration: 28 | 1 to 41 |
| Treatment period 8 week | Days after the Administration: 56 | 42 to 70 |

< Other than FMD >

| Visit | Reference implementation date | Time Allowance |
|---------------------------|-----------------------------------|-------------------------------|
| | | Days after the Administration |
| Start of Treatment Period | Days after the Administration: -1 | -29 to -1 |
| Treatment period 4 week | Days after the Administration: 28 | 1 to 41 |
| Treatment period 8 week | Days after the Administration: 56 | 42 to 70 |

- The reference implementation date and the number of days after administration in the treatment period are indicated as “Day -1” for the day before study drug administration and “Day 1” for the administration day. As the administration is started from the day after the visit, 4 weeks of the treatment period and 8 weeks of the treatment period are 28 days and 56 days after the study drug administration.

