9. LISTING

Following lists will be create for randomized subjects.

- Demographics
- Discontinuation
- Protocol Deviation
- Subjects Excluded from Analyses

- Compliance of Study Drug Administration
- Adverse Event
- FMD Test
- Laboratory Tests (Blood biochemical examination including 4h postprandial)
- Laboratory Tests (Blood biochemical examination and urine test excluding 4h postprandial)

10. CONSIDERATIONS on STATISTICAL ANALYSIS

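### Safety values taken at discontinuation after Visit 3 but by Day 41 can be missing from every summary and shift table, because they compete with Visit 3 for one Week 4 slot

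*SAP*

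**What the plan says.** For data other than FMD, SAP 2 defines two post-dose windows: "Days after the Administration: 28 | 1 to 41" for Week 4 and "Days after the Administration: 56 | 42 to 70" for Week 8. When a window holds more than one value, "the one with the closest inspection date, observation, and evaluation date to the reference date is adopted"; a tie goes to the more recent one. There is no discontinuation window.

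SAP 8.2.1 (weight, blood pressure, pulse) and SAP 8.2.2 (FPG) use the same three time points: "Visit: Start of Treatment Period, Treatment Period 4 week and 8 week". Summaries, changes from baseline and shift tables are all built on these; the last are specified as "shift tables of start of treatment period and each visit of treatment period 4 week and 8 week will be prepared". Neither section has a discontinuation or last-value row.

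The protocol collects these measures when a subject stops. Protocol 9.3.4 asks that such subjects, as far as possible, "undergo tests, observations, and evaluations required for the last visit within 3 days from the last dose taken"; its list includes vital signs, which Protocol 9.1.5 defines as blood pressure and pulse, and laboratory tests. Body weight is not named in 9.3.4. It is marked in the discontinuation column of Appendix A, in the edition that includes the exploratory biomarker panels (taken here as current).

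SAP 9 begins "Following lists will be create for randomized subjects" and names FMD and laboratory listings, but none for vital signs or weight. SAP 10.2, on dropouts and missing data, contains only a rule for values below the quantitation limit.

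**The concern.** Weight, sitting blood pressure, sitting pulse and FPG are named safety endpoints (Protocol 5.2.4). Keeping the value nearest the nominal day suits a by-visit comparison of subjects who stay on schedule. Applied unchanged to safety, it can remove the last value recorded in a subject who stopped, solely because that value was taken further from Day 28 than the Visit 3 value.

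At stake is whether the tables show all the safety data collected from early stoppers. A blood pressure reading at discontinuation that was not reported as an adverse event could appear in no planned output.

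**Working it through.** The plan gives no figure on this point, so there is none to reproduce. The check applies the SAP 2 rule to every possible pair of days.

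**Inputs**
- Week 4 window Day 1 to 41, reference Day 28; nearest value kept, ties to the later value (SAP 2).
- Visit 3 allowed on Day 14 to 41, scheduled Day 28 (Protocol 9.3.3, Appendix A).
- Discontinuation assessment up to 3 days after the last dose, where possible (Protocol 9.3.4, Appendix A).

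**Rule.** Let Visit 3 be on day v and the discontinuation assessment on day d, with v < d ≤ 41. Both fall in the Week 4 window. The discontinuation value is kept only if |d − 28| ≤ |v − 28|.

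- If v ≥ 28, every later d is further from Day 28, so the discontinuation value is always dropped.
- If 15 ≤ v ≤ 27, it is kept for d ≤ 56 − v and dropped for the remaining v − 15 of the 41 − v possible days.
- If v = 14, it is never dropped.

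**Single Visit 3 days**

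| Visit 3 day | Dropped / possible days | Share |
|---|---|---|
| 14 | 0/27 | 0% |
| 15 | 0/26 | 0% |
| 21 | 6/20 | 30% |
| 24 | 9/17 | 53% |
| 25 | 10/16 | 63% |
| 27 | 12/14 | 86% |
| 28 | 13/13 | 100% |
| 35 | 6/6 | 100% |

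**Assumed ranges for Visit 3**

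| Visit 3 range | Dropped / pairs, all pairs equal | Each Visit 3 day equal |
|---|---|---|
| Day 25 to 31 | 79/91 = 87% | 89% |
| Day 21 to 35 | 139/195 = 71% | 79% |
| Day 14 to 41 | 169/378 = 45% | 65% |

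The last row is the sum of 78 dropped pairs for v = 14 to 27 and 91 for v = 28 to 40. Whenever the discontinuation value is kept, the Visit 3 value is dropped instead.

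**Wider denominator.** If stopping assessments run from the day after Visit 3 to Day 55, those on Day 42 or later enter the Week 8 window. The dropped share is then 13/27 = 48% for Visit 3 on Day 28, 42% for Day 25 to 31 and 35% for Day 21 to 35 (each Visit 3 day weighted equally).

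**Number of subjects.** A dropped discontinuation value always lies on Day 29 to 41, which is 13 days. The documents give no dropout rate. Assume 5% to 20% of 40 subjects stop (2 to 8), with assessment days uniform over Day 1 to 55:
- 2 × 13/55 = 0.5 subjects
- 8 × 13/55 = 1.9 subjects

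This is the expected number assessed on those days, and so an upper limit on the number dropped under the assumption.

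**Other handling.** If the discontinuation assessment were treated as a visit of its own instead of being assigned by day, it would have no row in SAP 8.2.1 or 8.2.2 at all. Starting the Week 4 window at Day 14, as the protocol does for Visit 3, would change nothing, since Day 29 to 41 lies in both windows.

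**The case against.** A reader might infer that the rule makes both dose arms look safer than the collected data show. The documents do not support that. SAP 2 selects on date and never on the value, and a discarded reading may be better, worse or unchanged. Subjects also stop for reasons unrelated to tolerability (Protocol 7.5). What is shown is loss of information.

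A reader might also infer that the discontinuation value is usually lost. That holds when Visit 3 is near or after Day 28. When Visit 3 is on about Day 23 or earlier, the Visit 3 value is more often the one dropped.

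The rest of the case for leaving the plan alone is as follows:
- **The SAP follows the protocol.** Protocol 13.1.4 asks for summaries, changes and shift tables at Visits 3 and 4 against Visit 2, with no last-value row. This stands: the point is a gap, not a contradiction between the documents.
- **Adverse event reporting covers what matters.** Findings that lead to stopping the drug should be recorded under Protocol 10.1.3, and SAP 8.1.1 and 8.1.2 tabulate adverse events leading to discontinuation. This stands for events the investigator reports. It does not cover a change that the investigator did not judge clinically problematic.
- **FPG is recoverable.** It should appear in the laboratory listing of SAP 9. This stands and weakens the point for SAP 8.2.2. No such listing exists for blood pressure, pulse or weight, and the individual-data diagrams are specified by visit, so they are not a clear rescue.
- **Few subjects are affected**, and discontinuation assessments are made only where possible. This stands.

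**Conclusion.** The point holds as a limited defect that should be corrected. The plan's own selection rule can remove collected safety-endpoint values of early stoppers from every summary, change and shift table, and SAP 10.2 does not bring them back.

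The mechanism follows from the text alone. For assessments by Day 41, the loss is certain if Visit 3 is on Day 28 or later; all other shares depend on the visit-day distributions assumed above. The count of one or two subjects depends on an assumed dropout rate.

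Adverse event tables are unaffected. Subjects who stop before Visit 3, or who are assessed on Day 42 to 70, still have a slot. The gap matters most for blood pressure, pulse and weight, which have no listing.

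**What to change.** - In SAP 8.2.1 and 8.2.2, add a row for the last value on treatment, including the discontinuation assessment, to the summary, change and shift tables. Draw it from all post-dose values, without the nearest-to-reference rule.
- Keep SAP 2 for the by-visit rows.
- In SAP 9, add a listing of all collected vital signs and body weights.

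A worst-value row is not needed. Taking the worst of several readings shifts results toward deterioration by construction, which is hard to interpret without a control group (Protocol 6.2). If one is wanted, it should be optional, with the direction of worst stated for each parameter.

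The cost is SAP wording, one extra row per table and one listing. No new data are needed.

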8.2.2. Laboratory Test

Analysis Set: Safety Analysis Set

Analysis Variables: Fasting Plasma Glucose (FPG)

Visit: Start of Treatment Period, Treatment Period 4 week and 8 week

Analysis Methods: The following analysis is performed for Safety Analysis Set.

- (1) Summary statistics of measurements by treatment group at each visit during the treatment period will be calculated and a diagram of the change of individual data will be created.
- (2) The change for each treatment group (Treatment Period 4 week/8 week – Start of Treatment Period) will be calculated at each visit during the treatment period and the same analysis as in (1) will be performed.
- (3) Regarding evaluation results based on standard values, shift tables of start of treatment period and each visit of treatment period 4 week and 8 week will be prepared.

9. LISTING

Following lists will be create for randomized subjects.

- Demographics
- Discontinuation
- Protocol Deviation
- Subjects Excluded from Analyses

- Compliance of Study Drug Administration
- Adverse Event
- FMD Test
- Laboratory Tests (Blood biochemical examination including 4h postprandial)
- Laboratory Tests (Blood biochemical examination and urine test excluding 4h postprandial)

10. CONSIDERATIONS on STATISTICAL ANALYSIS

10.1. Adjustments for Covariates

In the analysis for primary endpoint for Full Analysis Set, stratified analysis of %FMD (fasting) is performed with Fasting TG value ($150 \leq - < 200$, $200 \leq - < 500$) at the start of treatment as a layer. Details are described in 7.1 (3) and (4).

10.2. Handling of Dropouts or Missing Data

For laboratory test, values below quantitation limit are treated as zero.

10.3. Criteria for Interim Analysis and Early Discontinuation

Interim analysis will not be performed

10.4. Multicenter Studies

Analyses for consideration of medical institution will not be performed.

10.5. Multiple Comparisons/Multiplicity

It does not adjust multiplicity.

10.6. Examination of Subgroups

Subgroup analysis will not be performed.

11. REVISION HISTORY

| Ver. | Date | Author | Revised Content | Reason for Revision |
|------|-------------|--------|--|--|
| 1.0 | 23 May 2016 | PPD | - | |
| 2.0 | 4 Aug 2016 | PPD | [2.TIME WINDOW] Add <Exploratory biomarker evaluation> Add 7.3.2. Exploratory evaluation item (exploratory biomarker evaluation) | For exploratory evaluation item addition |
| 3.0 | 29 Aug 2017 | PPD | [Title page] Modify affiliation of approver and biostatistics manager. | For organization change and company integration |
| | | | [2.TIME WINDOW] Delete <Exploratory biomarker evaluation> Delete 7.3.2. Exploratory evaluation item (exploratory biomarker evaluation) | Analysis of exploratory biomarker is performed after March in 2018 |
| | | | [5 OTHER DATA HANDLING] Add “Non-serious Adverse Event” | As required by Clinical Trial.gov |
| | | | [6.1.3 Subject Disposition] Change of Analysis Variables (“Exit Status of Stud Drug” → “Exit status from the study” | For mistake correction |
| | | | [7.1. Primary Endpoint and the Analytical Methods] Add analysis of Complete Case | To study as sensitivity analysis |
| | | | [8.1.1. Brief Summary of Adverse Events] [8.1.2. Display of Adverse Event] Add “Non-serious Adverse Event” | As required by Clinical Trial.gov |

| | | | | |
|-----|-------------|-----|--|--|
| | | | [10.2. Handling of Dropouts or Missing Data] Add handling of values below quantitation limit in laboratory test | To clarify the definition of handling below quantitation limit |
| 4.0 | 14 Nov 2017 | PPD | [Title page] Modify affiliation of biostatistics manager. | For organization change |
| | | | [5. OTHER DATA HANDLING] Add < Data Handling for Duration of Dyslipidemia (year)> | To clarify the specification |
| | | | [General] Correct stratification factor from " Fasting TG at the Start of Treatment" to "Fasting TG at Observation Period" | Due to the data review, stratification factor was found to be " Fasting TG at Observation Period " |
| | | | [7.2. Secondary Endpoints and the Analytical Methods] “the same analyses describes in 7.1 are performed by visit” → “the same analyses describes in 7.1 (1) - (4) are performed by visit” | Analysis for complete case is performed only for primary endpoint. |
| | | | [9. LISTING] Add list to be created | For creation of lists |
